7.1 Sample Size Considerations

The sample size estimation was determined based on demonstrating equivalence between the Test (T) product (Lupin Tiotropium Bromide Inhalation Powder) and the Reference (R) product (SPIRIVA HANDIHALER) for the primary endpoint change from baseline in FEV₁ AUC₀₋₂₄ on the treatment day, and to demonstrate that both the Test (T) and Reference (R) products are superior to the placebo. Bioequivalence (BE) will be demonstrated if the 90% confidence interval (CI) on the T to R ratio for the endpoint is contained within the interval (0.80, 1.25). Superiority will be demonstrated by showing that each active treatment's response for the endpoint is greater than, and statistically different from ($p < 0.05$, two-sided), that of the placebo (P). For the equivalence evaluation, the results in the PP analysis set will be considered definitive and for the superiority evaluations, those in the Intent-to-Treat (ITT) population will be considered definitive.

A review of the literature did not yield any estimates of within-patient variability of baseline-adjusted FEV₁ AUC₀₋₂₄ from a crossover study using a similar patient population with similar objectives. From a review of studies on clinicaltrials.gov, there were a number of estimates available of between-patient variability for baseline-adjusted FEV₁ AUC₀₋₂₄. From the 12 studies reviewed, the mean coefficient of variation (CV) for the variable was 121%. Within-patient variability is generally much less than between-patient variability. As a starting point for the sample size estimation it was assumed that the within-patient variability would be about 50% of the between-patient variability, or a CV of 60%.

The goal of the study is to complete 180 patients per protocol. With a sample size in each of the 6 sequence groups of 30, for a total sample size of 180, a crossover design will have 90% power to reject both the null hypothesis that the ratio of the test mean to the standard mean is below 0.80 and the null hypothesis that the ratio of test mean to the standard mean is above 1.25 (ie, that the test and standard are not equivalent), in favor of the alternative hypothesis that the means of the 2 treatments are equivalent, assuming that the expected ratio of means is 1.00, the between-patient CV is 1.21, the intra-patient CV is 0.60. In order to allow for a potential 30% premature withdrawal rate or loss from the PP population due to protocol deviations, 240 patients will be randomized in total, 40 to each of the 6 treatment sequences.

As no estimates of within-patient variability were available in the public domain, a blinded interim analysis will be conducted in order to assess the within-patient variability. The blinded interim analysis will be done to ascertain if an increase in sample size is necessary maintain 90% power to complete the study with a 90% CI for the relative bioavailability of the Test (T) to the Reference (R) product inside of the pre-specified interval 0.80-1.25. The blinded interim analysis will be discussed in [Section 11.0](#).

Sponsor: Lupin Inc.
Protocol no: TB-DPI-301

7.2 Randomization

Patients will be randomly assigned to the treatment sequences by means of a computer generated randomization list after confirmation of all eligibility criteria. The randomization list and study medication will be assigned via interactive response technology (IRT). Y-Prime Inc. will be responsible for generating the randomization schedule.

The randomization scheme utilized in TB-DPI-301 will be central. A total of 240 patients will be randomized in a ratio of 1:1:1:1:1:1 to the 6 treatment sequences based on a Williams design Latin square in the cross-over design shown in [Table 1](#).

Additionally, on each study day, as this is a double-dummy study, the order of administration of the LUPINHALER and HANDIHALER will be assigned based on even/odd calendar days. On odd calendar days (eg, 1, 3, 5, 29, 31), the LUPINHALER will be dosed first. On even calendar days (eg, 2, 4, 6, 28, 30), the HANDIHALER will be dosed first.

A subset of approximately 120 patients (at select investigational centers) will be enrolled into the open-label phase of the study (Part 2). These patients will not be randomized and all patients in Part 2 will receive Lupin Tiotropium Bromide Inhalation Powder.

8.0 Study Variables

8.1 Primary Efficacy Variable

The primary variable is the baseline-adjusted FEV₁ AUC_{0-24h} on the single-dose treatment days. Baseline is defined as the average of the FEV₁ values recorded at approximately 30 minutes and 15 minutes before dosing with study medication.

8.2 Safety Variables

Safety will be assessed throughout Part 1 and Part 2 of the study by monitoring the following:

- adverse events (AEs)
- SABA (albuterol/salbutamol MDI) and concomitant medication use
- vital signs measurements
- physical examinations
- head, ears, eyes, nose, and throat (HEENT) and chest examinations
- COPD exacerbations
- 12-lead electrocardiograms (ECGs)
- Laboratory (screening only)
- ER-S: COPD Scores
- Safety Spirometry

8.3 Other Variables

For a subset of the LUPINHALERS used during the open-label extension (Part 2), the following endpoints will be assessed:

- ruggedness of the LUPINHALER during 72 days of in-patient use:
 - percent (%) of overall inhalers with reported problems or malfunctions; comprised of misuse episodes (eg, impact and moisture) and issues identified (eg, mechanical problems and COPD worsening/seems ineffective) during 72 days of in-patient use
- in vitro performance of 100 inhalers post 72 days of in-patient use
The data resulting from the in vitro evaluation of the pharmaceutical performance will be presented in a separate report.

9.0 Definitions

9.1 Baseline and Change from Baseline

Baseline is defined as the last observation prior to dosing. Generally, baseline in Part 2 of the study will be the same as baseline in Part 1 of the study unless otherwise specified. For the primary variable (FEV₁ AUC_{0-24h}), baseline is defined as the average of the FEV₁ values recorded at approximately 30 minutes and 15 minutes before dosing with study medication.

Change from baseline = post-baseline value – baseline value.

9.2 Baseline-adjusted FEV₁ AUC_{0-24h}

The baseline-adjusted FEV₁ AUC_{0-24h} is defined as the baseline-adjusted area under the curve for forced expiratory volume in 1 second from time zero to 24 hours postdose using the trapezoidal rule based on actual time of measurement.

The baseline FEV₁ will be the average of the 2 predose FEV₁ measurements (30 minutes and 15 minutes pre-dose) at the clinic visit. If one of the predose FEV₁ measurements is missing, or excluded due to poor quality spirometry effort, the other non-missing measurement will be used as baseline. If both predose FEV₁ measurements are missing or excluded, baseline will be treated as missing.

Baseline-adjusted FEV₁ will be calculated as postdose FEV₁ after subtracting the baseline FEV₁ value.

[figure not shown]
The general area under the concentration-time effect curve (AUC) formula by the trapezoidal rule is given below:

$$AUC_{(0-t_n)} = \sum_{i=1}^n \frac{c_i + c_{i-1}}{2} (t_i - t_{i-1})$$

Sponsor: Lupin Inc.
Protocol no: TB-DPI-301

where t_n is the maximum time, n is the number of time points, and c_i is the change in FEV₁ from baseline at time t_i . For AUC calculations t_0 will be the start time of dose administration ($t_0=0$), and c_0 will be 0. AUC calculations will utilize the actual time of spirometry measurements.

Note- the area under the curve that is the primary variable is the area between the baseline value (straight red line and the curve). It is NOT measured from the x-axis.

9.3 Treatment, Washout and Follow-up

For summary purposes, treatment will be defined as days of dosing and days immediately after dosing, eg, day 0, 1, 21(+3), 22, 42(+3) and 43; washout will be days between treatments; follow-up is defined as 7 ± 3 days after visit 4 for Part 1, for patients who did not enter into the open-label Part 2 extension.

For Part 2, treatment is defined as first dosing date in Part 2 until the end of study or early termination (ET) for Part 2; follow-up is defined as 7 ± 3 days after visit 10.

9.4 Double-blind Period vs. Open-label Period

The double-blind period is defined as Part 1 of the study, from randomization to visit 4 or early termination before visit 4. For those who do not participate in Part 2 of the study (open-label), it also includes the follow-up period, which is 7 ± 3 days after visit 4.

Open-label period is defined as Part 2 of the study, from enrollment in Part 2 (open-label) to the end of Part 2 study or ET from Part 2. It also includes the follow-up period, which is 7 ± 3 days after visit 10.

9.5 Treatment Emergent Adverse Event (TEAE)

AEs will be summarized separately for TEAEs and Non-TEAEs.

Non-TEAEs are AEs observed after signing ICF until the initiation of the dose of the first experimental treatment.

A TEAE is defined as an event with an onset date/time on or after the initiation of the dose of the first experimental treatment after randomization or an event that is present at the initiation of the study medication and that subsequently increases in severity or frequency. AEs with a missing onset date and a stop date on or after 1st Dose Date or with a missing stop date, will be summarized as TEAEs.

9.6 Serious Adverse Event (SAE)

An SAE is defined as an AE that results in any of the following:

- death
- life-threatening
- requires hospitalization or prolongs existing hospitalization
- results in persistent or significant disability or incapacity
- results in a congenital abnormality or birth defect
- an important medical event which requires medical intervention to prevent any of the above outcomes

9.7 Spirometry (Part 1 Only)

FEV₁

The spirometry endpoint data will be captured using standardized equipment supplied by a central spirometry vendor - ERT.

All visits to the investigational center for Part 1 must be scheduled in the mornings between 0600 and 1000 and spirometry testing should begin at ± 1 hour of the start of visit 1 study qualifying spirometry testing time. Predose FEV₁ measurements will be recorded at 0 hours (-30 and -15 minutes before administration of study medication) at the investigational center at visits 1 through 4; serial FEV₁ measurements will be recorded postdose at 5 and 30 minutes, and at 1, 2, 4, 6, 8, 10, 12, 23, and 24 hours.

The following windows are permitted: +5 minutes for predose measurements (-30 and -15 minutes) and 5 minute postdose measurement; ± 5 minutes for 0.5-6 hours, and ± 15 minutes for 8-24 hours.

Reversibility Testing

For reversibility testing, patients will receive 68 mcg of ipratropium bromide inhalation pMDI as 4 actuations of 17 mcg/actuation (ex-mouthpiece); given at approximately

Sponsor: Lupin Inc.
Protocol no: TB-DPI-301

30 second intervals. If required, spacers are permitted for use during reversibility testing for ipratropium bromide administration. All actuations are to be completed within 3 minutes of the 1st actuation. The ATS/ERS criteria will be followed for spirometry measures. Patients who do not demonstrate a positive improvement of at least 15% in FEV₁ measured at 30 or 60 minutes (± 5 minutes) post inhalation will not be eligible to participate in the study (except as permitted per the retest specified below). Reversibility values of 14.50-14.99 will be rounded to 15. Refer to the spirometry manual for additional information related to reversibility testing. Patients failing to meet the reversibility requirement will be permitted to retest once, based on Investigator judgment (for only those patients who would normally achieve this level of reversibility) no sooner than 24 hours and no later than 2 weeks after the initial failure.

FEV₁ Stability Limits

FEV₁ stability limits will be calculated for each patient at the screening visit (visit 1) using the onsite spirometer and the randomization visit (visit 2), using both the home device and onsite spirometer.

Screening Visit:

The stability limit established at the screening visit will be used to determine alert criteria for worsening COPD during the screening and run-in periods. The FEV₁ stability limit at the screening visit will be calculated as follows:

Best pre-bronchodilator qualifying FEV₁ measurement at the screening visit (visit 1) using the onsite spirometer $\times 80\%$.

Randomization Visit:

Two stability limits will be re-established at the randomization visit (visit 2) for use during the double-blind and open-label treatment periods using the following equations:

- Investigational Center Stability Limits (for use with onsite spirometer at the double-blind visits only): mean FEV₁ of the predose pre-bronchodilator qualifying FEV₁ measurements (-30 and -15 min) using the onsite spirometer $\times 80\%$
- At Home Stability Limits (for use with the electronic flow meter [home device]): mean of the best predose FEV₁ measurements on the last 3 days before randomization on the home device $\times 80\%$

If a patient falls below any of the above FEV₁ stability limits, an alert will be triggered to the patient and investigational center personnel.

Note: If the reschedule icon on the site spirometer is chosen for the screening visit (visit 1) or visit 2, and therefore, visit 1 or visit 2 is performed again, the FEV₁ stability limit will be updated accordingly. If V1_RETEST on the site spirometer is performed, the stability limit will not be updated.

9.8 Spirometry (Part 1 and 2)

Patients enrolled in Part 1 and Part 2 of the study will be issued with an eDiary/electronic flow meter to assess their lung function (FEV₁). FEV₁ collection begins at the time of signing the ICF, and then continues throughout Part 1 and Part 2, per the randomization scheme.

For Part 1, FEV₁ will be measured once daily: prior to dosing in the morning (if applicable) at approximately the same time each day. On days of the investigational center visits, spirometry will be performed using the equipment at the investigational center.

For Part 2, FEV₁ will be measured twice daily at home: upon awakening in the morning immediately prior to dosing with study medication and at 2 (+2) hours after study medication administration. Three (3) FEV₁ measures should be taken at each time point; the highest effort will be used.

9.9 COPD Exacerbations (Part 1 and Part 2)

A COPD exacerbation is defined as worsening of symptoms of COPD for at least 2 consecutive days and classified as mild when patients do not require treatment with systemic corticosteroids and/or antibiotics; moderate when treatment with systemic corticosteroids and/or antibiotics are required; or severe when hospitalization or visit to the emergency care/acute care unit is required. A separate exacerbation is considered when an interval of clinical improvement of at least 7 days is observed.

Any moderate or severe COPD exacerbation occurring during Part 1 will result in withdrawal.

COPD exacerbations will be documented separately from AEs on a COPD exacerbation log in the electronic case report form (eCRF), unless the exacerbation meets the definition of an SAE. In this instance, the exacerbation will be recorded on both the AE and COPD exacerbation pages of the eCRF.

Collection of COPD exacerbations will begin at the time of consent and will continue through the final visits in Part 1 and Part 2 of the study. COPD exacerbations will be captured via patient interview during the onsite or telephone visits.

9.10 COPD Symptom Scores (Part 1 and Part 2)

During Part 1 (commencing at the time of consent) and Part 2 of the study, patients will assess and record their COPD symptoms scores once daily in the evening before bedtime using the EXACT.

The EXACT is a 14-item daily diary designed to provide a direct measure of patient-reported symptoms of COPD exacerbation. The EXACT Total score is computed across the 14 items and has a theoretical range of 0 to 100, with higher values indicating a more severe condition. The total score is used in the determination of exacerbation frequency, severity, and duration of exacerbation.

Sponsor: Lupin Inc.
Protocol no: TB-DPI-301

All 14 items of the EXACT are to be completed by the patient each evening prior to bedtime, reflecting back on their experiences “today.”

The ER-S: COPD is a derivative instrument of the EXACT designed to address the need for standardized daily diary to assess respiratory symptoms in patients with COPD.

The ER-S: COPD is comprised of 11 respiratory symptom items contained in the 14-item EXACT. A daily Total score (RS-Total score) representing respiratory symptom severity, overall and 3 subscale scores (RS-Breathlessness, RS-Cough and Sputum, and RS-Chest Symptoms) can be computed from the E-RS. The daily RS-Total score is computed by summing the raw score assigned to each of the 11 items and has a theoretical range of 0 to 40, with higher values indicating more severe respiratory symptoms. The same simple summation procedure is used for obtaining the 3 daily domain scores of the E-RS: RS-Breathlessness is the sum of items 7, 8, 9, 10, and 11 (score range 0-17); RS-Cough and Sputum is the sum of items 2, 3, 4 (score range 0-11); and RS-Chest Symptoms is the sum of items 1, 5, 6 (score range 0-12).

The ER-S: COPD (derived from the EXACT score) will be used to assess disease stability throughout the study. A baseline score will be obtained from the first available evening session after the signing the ICF for use during the screening and run-in periods and from the latest available evening session before the randomization visit (visit 2) for use during the double-blind and open-label treatment periods. If at any time, there is increase in the ERS-COPD daily RS-Total score of ≥ 2 from baseline, the eDiary will alert the patient to notify the investigational center personnel to discuss the patient’s current health status. The Investigator will need to determine if the patient is able to continue participating in the study as per the withdrawal criteria.

9.11 Methods for Handling Dropouts and Missing Data

Missing efficacy data will be handled in the following ways:

For missing serial spirometry measurements:

Missing data methods will be used provided that at least 9 of the 11 post-dose serial spirometry measurements are available. Linear interpolation between the 2 adjacent FEV₁ measurements will be used to estimate missing spirometry measurements occurring between 2 available measurements. The exception to this would be the unlikely event of missing measurements that occur near the peak of the FEV₁ -time curve, expected to occur between 30 min to 2 hours post dose. In these cases the average percentage change from the preceding value for patients receiving the same treatment will be used. This makes use of the response of other patients to the same treatment. For analysis, the percentage will be expressed in terms of an FEV₁ value.

For missing measurements at the end of the time profile (i.e., no available FEV₁ value after a point in time):

- For values at the end of the profile that were missing because rescue medication was taken, the minimum observed FEV₁ value on that test day, including the predose

Sponsor: Lupin Inc.
Protocol no: TB-DPI-301

value, will be used as the estimate. This is similar to assuming that there would be no increase from baseline after the point that rescue medication was required.

- For values at the end of the profile that were missing for reasons unrelated to the patient's response to treatment, the average percentage change from the preceding values for patients receiving the same treatment will be used. This makes use of the response of other patients to the same treatment. For analysis, the percentage will be expressed in terms of an FEV₁ value.
- For values at the end of the profile that were missing for unknown reasons, the observed minimum FEV₁ value on the day of testing, including the pre-dose value, will be used as an estimate. This conservatively assumes that there would be no increase from baseline after the point that the data were missing.

Two additional sensitivity analyses will be performed, where the missing data rules for the tail end of the profile will be based on the following: (a) the AUC calculation will be based on the time interval up to the last non-missing time point, and will then be standardized by dividing by the length of time for which FEV₁ measurements were included (ie. the AUC will be a weighted average), and (b) the baseline value will be substituted for the missing values.

If a patient contributes data to at least 2 of the crossover legs, data from that patient will be included in the analysis as the patient will have provided data for one of the treatment comparisons. If a patient completes only 1 leg of the crossover, data from the patient will be listed but will not be included in summary statistics or the analysis. There is no reasonable basis for imputing data for a completely missing leg of the crossover.

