### 8.1.1 Washout Restrictions during Part 1 of the Study Only

The washout period for LAMA or LABA is as follows:

- LAMA medications (including mono products and combination products containing LAMAs [eg, LAMA/LABA]) will not be permitted within 21 days of the screening visit (visit 1) and throughout the study (except for the study medication provided at each treatment period). Any patients taking LAMA medications will need to discontinue these medications, and at the Investigator's discretion, the LAMA may be replaced with ipratropium bromide (SAMA), adhering to the washout restrictions below.
- LABA mono products will need to be discontinued 7 days before the screening visit (visit 1) and throughout the study. Any patients taking LABAs will need to discontinue these medications, and at the discretion of the Investigator, the LABA may be replaced with ipratropium bromide (SAMA), adhering to the washout restrictions below.
- ICS/LABA combination products will need to be discontinued 30 days before the screening visit (visit 1) and throughout the study. Any patients taking

ICS/LABAs will need to discontinue these medications, and at the discretion of the Investigator, the ICS/LABA may be replaced with ipratropium bromide (SAMA), adhering to the washout restrictions below

Patients should refrain from taking the following medications from the specified time points below prior to spirometry assessments at each clinic visit (both days of each inpatient visit) during Part 1 of the study:

- SABAs 6 hours
- SAMAs: 8 hours
- short-acting forms of theophylline: 12 hours
- twice-a-day controlled-release forms of theophylline: 24 hours
- once-a-day controlled-release forms of theophylline: 36 hours
- caffeine-containing medications (eg, MIDOL®, EXCEDRIN®) 6 hours

If a patient requires the use of a SABA for rescue during the serial spirometry, the administration of the rescue medication should be recorded as a protocol deviation and the patient should continue with the pulmonary function testing as scheduled for that day.

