## 11 DATA COLLECTION AND ANALYSIS

This section describes the biostatistical analysis as foreseen at the time of planning the study. Changes, additions, and further details about the analyses will be described in the Statistical Analysis Plan (SAP). The SAP will take precedence over the protocol in the case of discrepancy. After finalization of the SAP and unblinding, any additional analyses or changes to analyses that may be required will be fully disclosed in the clinical trial report.

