### 11.5.3 Missing Data

For missing serial spirometry measurements:

Linear interpolation between the 2 adjacent FEV1 measurements will be used to estimate missing spirometry measurements occurring between 2 available measurements. The exception to this would be the unlikely event of missing measurements that occur near the peak of the FEV1-time curve. In these cases the average percentage change from the preceding value for patients receiving the same treatment will be used. This makes use of the response of other patients to the same treatment. For analysis, the percentage will be expressed in terms of an FEV1 value.

For missing measurements at the end of the time profile (ie, no available FEV1 value after a point in time):

- For values at the end of the profile that were missing because rescue medication was taken, the minimum observed FEV1 value on that test day, including the predose value, will be used as the estimate. This is similar to assuming that there would be no increase from baseline after the point that rescue medication was required.
- For values at the end of the profile that were missing for reasons unrelated to the patient's response to treatment, the average percentage change from the preceding values for patients receiving the same treatment will be used. This makes use of the response of other patients to the same treatment. For analysis, the percentage will be expressed in terms of an FEV1 value. Two additional sensitivity analyses will be performed based on the following: (a) the AUC calculation will be based on the time interval up to the last non-missing time point and (b) the baseline value will be substituted for the missing values.
- For values at the end of the profile that were missing for unknown reasons, the observed minimum FEV1 value on the day of testing, including the predose value, will be used as an estimate. This conservatively assumes that there would be no increase from baseline after the point that the data were missing.

Additional sensitivity analysis may be performed and will be described in the study SAP.

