10.2 Per Protocol

The Per Protocol (PP) analysis population will be the primary analysis population used for the determination of BE between the Test and Reference products. The PP analysis population will exclude patients from the ITT population who have major protocol deviations in Part 1 of the study on either the Test treatment day or the Reference treatment day. Patients may have a major protocol deviation on the Placebo treatment day and still be

Sponsor: Lupin Inc.
Protocol no: TB-DPI-301

included in the Per Protocol population that will be used to assess BE although data from the Placebo day will be excluded from the analysis.

All patients with a major protocol deviation will be identified before the study blind is broken, and the removal of a patient from a treatment period will be documented within the clinical trial management system's protocol deviation file. In addition, individual FEV1 values from a patient may be removed from their 24-hour serial curve, including the 2 predose measurements, if they were the result of poor quality spirometry efforts. In those cases, the value will be set to missing and missing value rules applied as described in [Section 9.11](#).

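### The SAP's 9-of-11 readings condition blocks its own no-benefit rule when readings are missing from before 12 h through 24 h because of rescue or for unknown reasons

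*SAP*

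**What the plan says.** SAP 9.7 schedules FEV1 "postdose at 5 and 30 minutes, and at 1, 2, 4, 6, 8, 10, 12, 23, and 24" hours. SAP 9.11 then sets a condition: "Missing data methods will be used provided that at least 9 of the 11 post-dose serial spirometry measurements are available". After it come interpolation for interior gaps, a separate rule near the peak, and three rules for tails. The first tail rule begins "For values at the end of the profile that were missing because rescue medication was taken". It fills those values with the lowest FEV1 of that day, predose included, which the SAP likens to assuming no gain over baseline from that point on. Tails missing for unknown reasons get the same value. Tails missing for reasons unrelated to response are filled from other patients on the same treatment.

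Protocol 11.5.3 carries the same rescue rule ("For values at the end of the profile that were missing because rescue medication was taken, the minimum observed" FEV1 of the day is the estimate) but asks for no minimum number of readings. Protocol 11 settles the difference: "The SAP will take precedence over the protocol in the case of discrepancy".

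Three other provisions bear on the point:

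- Protocol 8.1.1 records rescue during serial spirometry as a deviation and says "the patient should continue with the pulmonary function testing as scheduled for that day".
- SAP 10.2 allows poor-quality efforts to be removed: "In those cases, the value will be set to missing and missing value rules applied as described in" SAP 9.11.
- SAP 9.11 says of whole legs: "If a patient contributes data to at least 2 of the crossover legs, data from that patient will be included in the analysis". A leg that is missing altogether is not imputed.

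**The concern.** The rescue rule is there to give a poor score, not a blank, to a leg in which the patient needed help. The 9-of-11 condition withholds that score from the longest tails, which come from the earliest rescues, and grants it only to the shortest. What is lost then depends on response, and that is when leaving data out can bias a comparison. The unknown-reason tail has the same problem, although the SAP chose the same value for it and calls that choice conservative.

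At stake are the two superiority comparisons in the ITT population and the Test/Reference ratio in the PP population. SAP 13.6.4 requires all three to succeed.

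**Working it through.** **1. The count.** The scheduled readings are 5 min, 30 min, 1, 2, 4, 6, 8, 10, 12, 23 and 24 h. That is 11, matching the SAP's denominator. Those at or before 12 h number 9. If every reading after a rescue is missing through 24 h:

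| Rescue falls between | Readings left | At least 9? |
|---|---|---|
| dosing and 8 h (7 intervals) | 0 to 6 | no |
| 8 and 10 h | 7 | no |
| 10 and 12 h | 8 | no |
| 12 and 23 h | 9 | yes |
| 23 and 24 h | 10 | yes |

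The rule operates in 2 of 11 intervals and is blocked in 9, which together make up all of 0 to 12 h. For rescue between 12 and 23 h there is no slack: one earlier reading removed under SAP 10.2 leaves 9 − 1 = 8.

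**2. Does the condition reach the tail rules?** It stands before the separate lead-in for tails, so the layout leaves some doubt. SAP 11.4 points to yes: it applies the missing-data methods of section 9.11 at the interim and lists tail handling as an exception to them. The SAP's own term therefore includes the tail rules.

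**3. What the rule would have scored.** The day's lowest FEV1, predose included, cannot exceed baseline, so each imputed change from baseline is at most 0.

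**4. What happens to the leg instead.** The SAP does not say. There are two candidates.

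- *Dropped.* This fits the refusal to impute whole legs and the ITT requirement of a calculable endpoint. It also fits SAP 9.11 naming an AUC up to the last reading only as a sensitivity analysis.
- *Truncated under SAP 9.2*, whose sum runs to the maximum time. With the last reading at 10 h, the stated rule would have added (c10 + cmin)/2 × 2 + cmin × 11 + cmin × 1 = c10 + 13·cmin, where c10 is the change from baseline at 10 h and cmin the imputed change. If cmin is near 0, truncation differs from the rule only by about c10 × 1 h.

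So the material distortion comes from dropping.

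**5. Size, by assumption only.** Suppose affected legs have no benefit (mean 0), all other legs share one mean m, and each product's mean is a simple average of its available legs.

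| Affected legs, Test / Reference (assumed) | T/R, rule applied | T/R, legs dropped |
|---|---|---|
| 8% / 4% | 0.92m / 0.96m = 0.958 | 1.00 |
| 8% / 8% | 0.92m / 0.92m = 1.00 | 1.00 |
| 4% / 8% | 0.96m / 0.92m = 1.043 | 1.00 |

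The first row shifts the ratio by 0.042. The distance from the ratio of 0.90 assumed in SAP 11.5 to the 0.80 limit is 0.10.

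**6. Dependence on what follows a rescue.** Step 1 assumes readings missing through 24 h, the case the rule is written for. Two alternatives give different counts:

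- If only readings within 6 h of rescue were set to missing (an assumption that borrows the SABA withholding time in Protocol 8.1.1), rescue before 8 h leaves 8 or fewer. Rescue at 8 to 12 h leaves 9 or 10; that gap is interior and is interpolated, so the rescue rule is not used.
- If testing continues and every value is kept, 11 of 11 are available. Neither the condition nor the rule comes into play, and readings taken after a bronchodilator enter the AUC.

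**The case against.** The strongest objection is Protocol 8.1.1. Testing continues after rescue, and no SAP rule sets the later readings to missing. A reader might infer that every rescue before 12 h disables the rule; the documents do not support that. The point holds only when the readings are in fact missing through 24 h. The unknown-reason tail does not depend on Protocol 8.1.1.

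Second, bioequivalence is decided in the PP population, and rescue is already a deviation. If it is classed as major on a Test or Reference day, SAP 10.2 removes the patient whatever the reading count. SAP 13.2 leaves the major/minor classification to separate guidelines, so the PP effect is confined to rescues classed as minor and to unknown-reason tails.

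Third, a prespecified minimum of readings is a legitimate choice, and the SAP may add detail to the protocol. That stands for interior gaps and for tails unrelated to response. Measuring hours covered instead of counting readings would be a preference, and removing the count for interior gaps would ignore the SAP's exception near the peak.

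Fourth, the simple averages in the illustration are not the planned analysis. The repeated-measures model in SAP 13.6.1 uses a patient's other legs. If the same patients also do poorly there, the shift would be smaller.

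**Conclusion.** The point holds in a bounded form. Followed as written, SAP 9.11 withholds its no-benefit score when rescue-related or unknown-reason tails start before the 12 h reading and run through 24 h. The SAP gives no reason for narrowing the protocol's rule in this way and does not say how the leg is then analysed. The count is exact. That the condition covers tail values is a natural reading supported by SAP 11.4, and that the leg is dropped is an inference.

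Three further inferences are tempting but unsupported:

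- That the condition pushes T/R toward 1. Direction depends on which treatment loses more legs, and the 0.958 versus 1.00 comparison is purely assumed. In the superiority comparisons, lost placebo legs would work against the active products.
- That the 28 of 150 interim patients without three evaluable AUCs were lost this way. SAP 11.5 gives no reasons, and the interim carried the last observation forward in tails.
- That the two planned sensitivity analyses certainly cannot reveal the effect. They alter tail rules and would probably be subject to the same condition, but the text does not say so.

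**What to change.** In SAP 9.11, before unblinding:

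1. Exempt tail values missing because of rescue or for unknown reasons from the 9-of-11 condition, so that the stated minimum-FEV1 rule applies whatever the number of readings.
2. Keep the condition for interior gaps and for tails unrelated to response.
3. State how a leg with fewer than 9 readings is analysed.
4. Report the version with the condition applied to all tails as a sensitivity analysis.
5. Reconcile SAP 9.11 with Protocol 8.1.1 on whether readings after rescue are set to missing for the analysis.

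The cost is SAP wording and a small change to the AUC program. The downside is that some retained legs will rest on more imputed values; the sensitivity analysis in item 4 shows how much that matters.
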